1 BACKGROUND AND RATIONALE

As a global public health priority, there has been a pressing demand for the development and deployment of novel interventions to prevent and delay the onset of dementia. In recent years, Computerized Cognitive training (CCT) has garnered considerable evidence in improving the cognitive outcomes of individuals living with Mild Cognitive Impairment (MCI), a transitional stage between normal aging and dementia. The aim of this pilot study is to assess the feasibility and efficacy of CCT, specifically a multi-domain Virtual Reality Cognitive Training (VRCT) program on the cognition of individuals with MCI. The VRCT program will be conducted weekly over a period of 10 weeks for participants aged 65-85 with a diagnosis of MCI. 30 participants will be recruited from specialist outpatient clinics and they will be randomized into either the VRCT intervention group or the active control group. All participants will be assessed at baseline and post-intervention. We hypothesize favorable acceptability of the VRCT program. We also postulate positive changes on neuropsychological measures of attention, processing speed, memory and executive function following program completion. We expect these gains in cognition to be translated to improvements on secondary outcomes including mood and self-reported everyday memory functioning. In CGH, there is currently a lack of follow-up intervention options for patients who have received a diagnosis of MCI. Usual care procedures would include medication for risk factors as well as health advice for lifestyle factors such as exercise, diet and cognitively stimulating activities. If outcomes from this study prove to be positive, it will add to the evidence base of the novel application of Virtual Reality technology to Cognitive Training in a clinical setting. Furthermore, this will provide clinicians in CGH with an innovative intervention option to meet the needs of MCI patients in maintaining and enhancing their cognitive functions.

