4.2.2 Study Visits and Procedures

For Virtual Reality Cognitive Training Intervention Group:

- Visit 1 (Week 1): Pre-intervention neuropsychological testing (2 hours)
- Visit 2-11 (Weeks 2-11): Virtual Reality Cognitive Training (50 minutes per session)
- Final Visit (Week 12): Post-intervention neuropsychological testing (2 hours)

For Active Control Group:

- Visit 1 (Week 1): Pre-intervention neuropsychological testing (2 hours)
- Visit 2 & 3 (5 weeks apart): Psychoeducation and Cognitive Stimulation (1 hour per session)
- Final Visit (Week 12): Post-intervention neuropsychological testing (2 hours)

During the VR session and cognitive training, frequent checks will be performed to ensure that subject is comfortable. Should subject express fatigue or discomfort, session can be stopped and resume when subject is able to continue. The number of breaks will be recorded.

Appointment between sessions will be at least 7 days apart.

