7.3 Safety Monitoring Plan

The data and safety monitoring would be performed by the principal investigator and co-investigators. The data would be reviewed monthly or at the point of recruitment of every 10 subjects, whichever occurs first. Data that would be reviewed would include adverse events occurring during the intervention such as excessive patient agitation resulting in injuries or device dislodgements requiring termination of intervention.

15 subjects would be receiving intervention. If 8 or more subjects are unable to meet the composite end-point for completion of intervention, the study would be terminated.

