9 SAMPLE SIZE AND STATISTICAL METHODS

9.1 Determination of Sample Size

As this is a pilot study, there is no power calculation for the sample. Based on the funding available, we intend to recruit up to 30 participants.

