9.2 Statistical and Analytical Plans

Intention-to-treat analyses will be performed using the last observation carried forward method for subjects who were lost to follow-up or had missing data. Data will be analysed using IBM SPSS Statistics 26.0. Continuous variables will be presented as mean and standard deviation (SD) or median and interquartile range (IQR) where appropriate, while categorical variables will be presented as frequencies and percentages. A one-way analysis of variance will be conducted to assess the between-group difference of the intervention's effect over time for each outcome measurement. The significance level will be established at $p < 0.05$. Cohen's d effect size (ES) will be reported alongside the p-values, and thresholds of 0.2 for small, 0.5 for moderate, and 0.8 for large effects were employed as guiding benchmarks.

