14 RETENTION OF TRIAL DOCUMENTS

Records for all participants, including CRFs, all source documentation (containing evidence to study eligibility, history and physical findings, laboratory data, results of consultations, etc.) as well as IRB records and other regulatory documentation will be retained by the PI in a secure storage facility. The records will be accessible for inspection and copying by authorized authorities. Data will be kept for 7 years before secure destruction.

15 FUNDING and INSURANCE

This project has been awarded with the CGH GY2019/20 Innovation Grant amounting to \$20000. Upon completing of the project, the PI is required to submit a written final report and present the findings as required by the CGH Office of Innovation.

16 Results Summary

Participants in the VRCT group exhibited significant favourable changes in the RBANS figure copy ($p = 0.01$) and FAB go-no-go ($p=0.04$) subdomains over time as compared to the control group (Table 3). While not statistically significant, moderate to large ES favouring the VRCT group were observed in RBANS list recall (ES = 0.7) and RBANS figure recall (ES = 0.8). Small to moderate ES favouring the VRCT group were demonstrated in FAB (ES = 0.3), and FAB conflicting instructions (ES = 0.3).

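### Section 9.2 compares the arms without using each outcome's baseline score as a covariate; a labelled ANCOVA alongside the planned ANOVA would cost almost nothing

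*Combined protocol and SAP*

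**What the plan says.** Section 9.2 gives the only between-arm test: "A one-way analysis of variance will be conducted to assess the between-group difference of the intervention's effect over time", run on each outcome at the 0.05 level, with Cohen's d reported beside the p-value. Missing scores are filled "using the last observation carried forward method for subjects who were lost to follow-up or had missing data". No covariate, ANCOVA or mixed model appears in 9.2 or elsewhere. Section 9.2 does not say which variable enters the ANOVA, or which SD divides Cohen's d.

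The baseline data exist by design. Section 1 states: "All participants will be assessed at baseline and post-intervention". The visit lists in Section 4.2.2 put two hours of neuropsychological testing at Week 1 and again at Week 12 in both arms.

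On size, Section 9.1 says "we intend to recruit up to 30 participants" and Section 7.3 says "15 subjects would be receiving intervention". There is no power calculation. Section 2.1 makes effects on cognition, everyday memory and mood the second part of the primary objective.

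Section 16 already reports results. The VRCT group "exhibited significant favourable changes in the RBANS figure copy" subdomain, among others, over time against control.

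**The concern.** A one-way ANOVA has no time factor. With two assessments, the effect over time then reads most naturally as Week 12 minus baseline, and the wording of Section 16 fits that reading. A change score fixes the slope of Week 12 on baseline at 1. With equal SDs at the two visits the true slope is the correlation rho, which is below 1. Subtracting the whole baseline therefore over-corrects any chance difference between the arms, to the disadvantage of the arm that started higher, and it also adds variance.

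With about 15 per arm and many subscores, some outcomes will probably be imbalanced by chance. Section 1.2.1 says the pilot is meant to guide a later randomised trial, so the size and precision of the estimates are its main product. A reader given only the change-score result cannot tell how far it depends on where the arms started.

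**Working it through.** **Inputs.** From the documents: 15 in the VRCT arm (7.3); 15 controls, inferred from the maximum of 30 (9.1); two assessments (1, 4.2.2); alpha 0.05 (9.2). Assumed: normal scores, equal SDs at both visits (set to 1), and rho of 0.3 to 0.9. The plan states no power or precision figure, so there is none to reproduce.

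**Chance imbalance.** The baseline difference D has SD sqrt(2/15) = 0.365. Hence P(|D| > 0.35) = P(|Z| > 0.959) = 0.338. The 0.35 SD is only a reference size.

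**Variance factors** (each multiplied by 2/n gives the variance of the arm difference, n = 15):
- change score: 2(1 − rho)
- ANCOVA: (1 − rho²) × [1 + 1/(2n − 4)] = (1 − rho²) × 1.038, where the last factor is the price of estimating the slope.

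The 95% CI half-width is t × sqrt(factor × 2/15), with t = 2.048 on 28 df for change and 2.052 on 27 df for ANCOVA. Example at rho 0.5: change 2.048 × sqrt(1.000 × 0.1333) = 0.748; ANCOVA 2.052 × sqrt(0.779 × 0.1333) = 0.661.

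**Shift given D.** Change score: (rho − 1) × D. ANCOVA: about 0.

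| rho | Factor, change | Factor, ANCOVA | Variance saving | Half-width, change (SD) | Half-width, ANCOVA (SD) | Shift of change score at D = 0.35 (SD) |
|---|---|---|---|---|---|---|
| 0.3 | 1.400 | 0.945 | 32% | 0.885 | 0.728 | −0.25 |
| 0.5 | 1.000 | 0.779 | 22% | 0.748 | 0.661 | −0.18 |
| 0.7 | 0.600 | 0.530 | 12% | 0.579 | 0.545 | −0.11 |
| 0.8 | 0.400 | 0.374 | 7% | 0.473 | 0.458 | −0.07 |
| 0.9 | 0.200 | 0.197 | 1% | 0.334 | 0.333 | −0.04 |

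**Break-even.** ANCOVA has the lower variance when (1 + rho) × 1.0385 < 2, that is, for rho below 0.926.

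**Type I error** (simulation, no treatment effect, complete data, 100,000 runs per rho from 0.3 to 0.8). Over all randomisations both methods are close to 5%. Split by the imbalance that occurred:

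| rho | Change, \|D\| > 0.35 | Change, \|D\| ≤ 0.35 | ANCOVA, \|D\| > 0.35 |
|---|---|---|---|
| 0.3 | 9.9% | 2.3% | 4.8% |
| 0.5 | 8.8% | 3.1% | 5.2% |
| 0.7 | 7.3% | 3.9% | 5.2% |
| 0.8 | 6.5% | 4.1% | 4.9% |

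At rho 0.9 the change-score error is about 5.7% in imbalanced samples, which leaves about (5.0 − 0.338 × 5.7)/0.662 = 4.6% in the rest.

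**Variations for rho 0.3, 0.5, 0.7, 0.8.**
- 12 per arm analysed: the inflation is 1.050, P(|D| > 0.35) is 0.391, and the savings are 32%, 21%, 11%, 6%.
- LOCF with a share m of Week-12 scores missing: the carried value equals baseline, so the correlation becomes m + (1 − m)rho. With 10% missing the savings are 29%, 20%, 10%, 6%; with 20% missing, 25%, 17%, 9%, 4%. Both assume missingness unrelated to arm or score.
- If the response were the Week-12 score alone, the shift would be +rho × D (+0.105 to +0.28 SD at D = 0.35). ANCOVA would then have the lower variance once 1 − rho² < 1/1.0385, that is, for rho above about 0.19.

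**The case against.** The planned analysis is not wrong. It is unbiased over randomisations and holds its 5% level, and the documents promise no power that it could fail to deliver. The raised error under imbalance is balanced by a conservative test in the other 66% of samples, and the documents give no baseline values to show which kind of sample this is. All of that stands, and it is why this is an improvement and not a correction.

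The size of the gain rests on a correlation that the documents do not give; near 0.9 it all but vanishes. Normality and a linear relation are doubtful for short-range items such as single FAB subdomains, where ceiling effects need checking. The LOCF scenarios assume missingness at random, although Section 4.3.1 ends participation for discomfort with the VR equipment, which would arise in one arm only. These points stand as limits on the figures.

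The ANOVA response is inferred, so the change-score magnitudes would not carry over to another reading. The recommendation would: ANCOVA also gains under the Week-12 reading for every rho shown.

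Finally, the p-values in Section 16 would remain as they are, and a 95% CI carries the same information as a test at 0.05. The addition therefore helps only if it is shown for all outcomes and read as an estimate with its uncertainty.

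**Conclusion.** The concern holds as a worthwhile, low-cost improvement, with medium confidence. Section 9.2 leaves unused a baseline score that is collected on everyone. At 15 per arm, ANCOVA would shorten the 95% CI by about 18%, 12%, 6% and 3% at rho 0.3, 0.5, 0.7 and 0.8, and would remove the shift tied to the baseline imbalance actually seen. At rho 0.9 there is practically no gain, and above about 0.93 a slight loss. This assumes a change-score response, roughly normal scores, equal SDs and a linear baseline relation.

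It does not make the pilot well powered, does not repair LOCF and does not bear on retention or adherence. It does not show that any result in Section 16 is wrong.

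**What to change.** - State in Section 9.2 the response analysed in the one-way ANOVA and the SD used for Cohen's d. Keep this ANOVA as the prespecified analysis.
- For each scored outcome, add an ANCOVA with the Week-12 score as response, randomised group as factor and that outcome's baseline score as covariate. Report the adjusted mean difference with its 95% CI.
- Label the ANCOVA as specified after results, show it beside the ANOVA for all outcomes, and give no second set of p-values.
- Check linearity and ceiling effects for short-range subscores before relying on the adjusted estimate.

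The cost is one residual degree of freedom (28 to 27), about 4% variance inflation at 15 per arm (5% at 12) and one extra results table. No new data are needed.

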While other VR programs have largely focused on a single cognitive domain, we aim to assess the effects of a broad-based VRCT program that targets multiple cognitive outcomes. As compared to single-domain CT intervention, multi-domain CT appeared to be more advantageous in maintaining treatment effects¹⁹. Notably, two high quality randomized controlled trials have demonstrated interesting neuroimaging outcomes where increases in hippocampal functional connectivity were observed following multi-domain CCT, which is postulated to prevent memory loss²⁰. To our knowledge, this research would be the first of its kind in Singapore, thereby contributing to the current evidence base on the efficacy of VRCT on enhancing the cognition of individuals with MCI. In the clinical setting, MCI patients in Changi General Hospital are offered a limited range of treatment and follow-up options after receiving their diagnosis due a lack of available interventions. Through this pilot feasibility study, we hope to introduce an innovative clinical service to target the cognitive health of our patients with MCI. We believe that the current feasibility study will provide us with useful information

in guiding us to conduct a randomized controlled trial for a VRCT group program as well as a longitudinal study in the future to evaluate the effects of VRCT in delaying the progression of MCI to dementia. We hope that this novel intervention will improve our clinical service, efficiency and reduce manpower needed to run cognitive interventions for our patients.

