2.1 Primary Objectives

Our primary objective is to (1): assess the retention and adherence rates of the VRCT intervention and (2) examine effects of VRCT on cognition, everyday memory performance and mood of older adults with MCI.

2.2 Potential Risks and Benefits:

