3.3 Inclusion Criteria

- Aged 65-85
- Diagnosis of MCI by a clinician in accordance to Petersen's criteria
- Ability to see and hear
- Ability to read and write in either English or Mandarin
- Mini-Mental Status Examination > 23

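### Section 9.2 tests every outcome at an uncorrected p < 0.05 with no primary efficacy measure or exploratory label, and section 16 then calls two subtests significant without qualification (minor)

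*Combined protocol and SAP*

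**What the plan says.** Section 9.2 runs one test per outcome and applies one threshold to all of them: the between-group "effect over time for each outcome measurement. The significance level will be established at" p < 0.05. It adds Cohen's d with benchmarks of 0.2, 0.5 and 0.8. It gives no testing order, no correction, no confidence intervals and no statement that the efficacy tests are exploratory.

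No other section names one efficacy measure as primary. The second part of the primary objective in section 2.1 is to "examine effects of VRCT on cognition, everyday memory performance and mood of older adults with MCI". Section 1 expects "positive changes on neuropsychological measures of attention, processing speed, memory and executive function", four domains without ranking, and calls mood and everyday memory secondary: "improvements on secondary outcomes including mood and self-reported everyday memory functioning". The plan does not state the number of tests.

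The study is described as a pilot feasibility study (sections 1.2.2 and 4) and has no power calculation (sections 3.1 and 9.1). Section 1 says of its results: "If outcomes from this study prove to be positive, it will add to the evidence base". Section 1.2.1 expects the study to help "in guiding us to conduct a randomized controlled trial for a VRCT group program".

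Section 16 reports changes favouring VRCT in RBANS figure copy (p = 0.01) and FAB go-no-go (p = 0.04) as significant and refers to Table 3. It names four further measures: RBANS list recall and RBANS figure recall, described as not statistically significant, and FAB and FAB conflicting instructions, given with effect sizes of 0.3 and no p-values.

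**The concern.** When every outcome is tested at 0.05 and none is singled out, 0.05 is the error rate of each test and not of the set. The chance that something crosses the line grows with the number of tests. A reader of section 16 is told that two subtests were significant. The prose does not say that the p-values are uncorrected, how many tests lay behind them, or that no measure had been chosen in advance to carry the efficacy question.

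At stake is how much the two results can bear. Effects on cognition, memory and mood are part of the primary objective, and section 1 looks ahead to what a positive outcome would support. A nominal p-value on a subtest is a reason to look again. As printed, it reads as a finding.

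**Working it through.** **Inputs**
- Per-test level: 0.05 (section 9.2). Tests are taken as two-sided, so 0.025 of the error falls in the direction favouring VRCT. Sidedness is not stated; this is an assumption.
- Number of tests, k: 6, the measures named in section 16. This is a minimum.
- Reported p-values: 0.01 and 0.04 (section 16).
- Correlation r between test statistics: not in the documents. Assumed 0, 0.3 and 0.5.

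The plan has no power figure or familywise error rate to reproduce. For a single test, 1 − 0.95^1 = 0.05, the plan's own threshold.

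**Error rates with no true effect, independent tests, k = 6**
- At least one false positive, either direction: 1 − 0.95^6 = 0.265.
- At least one favouring VRCT: 1 − 0.975^6 = 0.141.
- Two or more favouring VRCT, the pattern in section 16: 1 − 0.975^6 − 6 × 0.025 × 0.975^5 = 0.0088.

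**With correlation.** Each test statistic is modelled as √r × (shared normal) + √(1 − r) × (own normal), and those beyond 1.96 are counted.

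| k = 6 | r = 0 | r = 0.3 | r = 0.5 |
|---|---|---|---|
| At least one, either direction | 26.5% | 24% | 21% |
| At least one favouring VRCT | 14% | 12% | 10% |
| Two or more favouring VRCT | 0.9% | 2.3% | 3.0% |

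Section 16 treats go-no-go and conflicting instructions as parts of FAB, so some tests must be correlated. The r = 0 column is therefore the upper end for the first two rows and the lower end for the third.

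**Effect of a larger count.** If mood and everyday memory were tested once each, as section 2.1 implies, k is 8. The three rows become 25% to 34%, 13% to 18%, and 1.6% to 4.3%.

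**Holm over six, for illustration**
- Figure copy, if it is the smallest p-value: 6 × 0.01 = 0.06. The printed 0.01 could be anything from 0.005 to 0.015, which gives 0.030 to 0.090. It passes only if the unrounded value is at most 0.05 / 6 = 0.0083.
- Go-no-go, if it is the second smallest: 5 × 0.04 = 0.20. Rounding (0.035 to 0.045) gives 0.175 to 0.225.
- Section 16 gives no p-values for FAB and conflicting instructions. Go-no-go does not depend on them: list recall and figure recall are stated to be non-significant, so at least two p-values are larger and its multiplier is at least 3. Even then 3 × 0.035 = 0.105, above 0.05.

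**The case against.** The strongest reply is that this is a pilot. Retention and adherence come first in section 2.1, there is no power calculation, and leaving pilot efficacy tests uncorrected is common and defensible. Section 9.2 also plans Cohen's d beside the p-values, and section 16 uses it. All of that stands, and it is why the point is minor and why a correction is not asked for as a matter of course. It does not remove the point. A pilot label on the study is not an exploratory label on its p-values: section 9.2 still sets a threshold, and section 16 still uses it to declare results.

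Table 3 may list every measure and p-value. That is fair. The criticism of the reporting is confined to the prose of section 16, and six is used only as a floor.

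Three stronger readings are tempting and are not supported:
- A reader might infer that the two results are probably false positives. The working says otherwise: two or more favourable results by chance are uncommon at six tests.
- A reader might infer that neither result survives correction. That holds for go-no-go. For figure copy the printed p-value is too coarsely rounded to tell.
- A reader might infer that one nominal result would make the study positive or fix the endpoint of the later trial. No section says so. The only numerical decision rule, in section 7.3, concerns completion of the intervention.

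The differing ranks given to mood and everyday memory in sections 1 and 2.1 are a separate specification matter and add no weight here.

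**Conclusion.** The point holds and is minor. The plan's rule leaves the error rate over the set of efficacy tests uncontrolled and unstated, and section 16 reports two subtests under that rule without qualification. At six tests and no true effect, some false positive would appear about 21% to 27% of the time, and one favouring VRCT about 10% to 14%, against 5% and 2.5% for a single two-sided test. These figures rest on two-sided testing, on assumed correlations of 0 to 0.5, and on a count of six that the full set of tests may exceed. They describe the procedure and do not show that either reported effect is absent. Both p-values should be read as nominal.

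**What to change.** **Section 9.2.** Label the cognitive, memory and mood tests exploratory. Commit to a 95% CI and the analysed n for every measure tested, favourable or not, beside the Cohen's d already planned.

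**Section 16, and any publication.** Replace the word significant with a description such as nominal, uncorrected, exploratory p-value. State how many tests were run, or point to Table 3 if it shows this. Say openly that the label was added after the results were known; it cannot restore prespecification.

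**Only if the p-values are to support efficacy claims.** Apply Holm over the full set of tests, using unrounded p-values.

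The cost is wording and intervals for analyses already run, with no new data. The real downside is that the headline of two significant subdomains is lost.
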